7.1.5 Three Weeks Post-randomisation Visit – Visit 5 (Day 35)

The following procedures are to be completed during the 3 Weeks Post-randomisation Visit at time points outlined on the Schedule of Assessments ([Appendix 2](#)).

- Record current medications
- Measure and record vital signs (blood pressure, heart rate, and body temperature)
- Complete full physical examination
- Complete the C-SSRS, BDI-II, BAI, PSQI
- Collect urine for pregnancy test in women of childbearing potential
- Draw blood for analysis of electrolytes (including sodium)
- Perform 12-lead ECG
- Collect unused study drug and perform drug accountability
- Dispense study drug

- Query for AEs including adverse events of special psychiatric interest

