Appendix 2: Schedule of Assessments

Visit Number	Visit 1 ⁽¹⁾	Visit 2 ⁽¹⁾	Visit 3	Visit 4	Visit 5	Telephone contact	Visit 6	Visit 7
Visit Name	Screening/ Placebo Run In	Eligibility assessment/ Randomization (start 10 mg litoxetine or Placebo BID)	1 week Post Randomization First dose escalation (start 20 mg or Placebo BID)	2 weeks Post Randomization Second dose escalation (start 30 mg or Placebo BID)	3 weeks Post Randomization		8 weeks post Randomization Final Treatment Visit⁽⁴⁾ (ET Visit)	13 weeks post Randomization Post-Treatment Safety F/U⁽²⁾ (End of Study Visit)
Study Day	Day 0	Day 14	Day 21	Day 28	Day 35	Day 42	Day 70	Day 105
Evaluation of eligibility/randomization	X	X						
Dispensing/collection of trial drug	X	X	X	X			X ⁽¹⁴⁾	X
Patient bladder diary review/collection ⁽¹²⁾	X	X					X	
Recording of AEs		X	X	X	X		X	X

Abbreviations: AEs = adverse events; BMI = body mass index; ECG = electrocardiogram; ET = early termination; PVR = postvoid residual urine volume; UTI = urinary tract infection

- (1) Eligible subjects will undergo a 2-week Screening Placebo Run-In Period with 7 days bladder daily diary symptom collection (e-diaries). Subjects who continue to be eligible after the Screening Placebo Run-In Period will be randomised (Treatment Period).
- (2) Visit window \pm 2 days
- (3) AEs must be followed for a minimum of 30 days and until complete resolution or stabilization of the event, or as deemed appropriate by the Investigator on consultation with the Sponsor medical responsible.
- (4) If a subject is withdrawn prematurely from the trial, all procedures indicated for the Week 8 (Visit 6) visit must be performed. The Investigator should use every effort to encourage the subject to taper study medication for 1 week and to return for the Safety Follow-up Visit (Visit 7).
- (5) Serum pregnancy tests will be performed prior to entry into the trial (Visit 1), the ET Visit (Visit 6; if the subject is discontinuing the study) and at the End of Study Visit (Visit 7) for all female subjects of childbearing potential. Only those female subjects with a negative pregnancy test at Visit 1 will receive trial medication.
- (6) Urine (dipstick) pregnancy tests will be performed at Visits 2, 3, 4, 5, and 6 (if it is not the ET Visit) for all female subjects of childbearing potential. Only those female subjects with a negative pregnancy test will receive trial medication.

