6.3 General Methodology

Safety

Safety data will be presented and analysed using the Safety Population.

The primary safety analyses include all treatment emergent adverse events defined as any AE started after Visit 2. The analysis will be carried out with point estimates and Clopper Pearson 95% confidence intervals.

Descriptive statistics will be provided for all variables in the summary tables by treatment group according to the type of variable summarised.

Quantitative variables will be summarised by using n (number of subjects per group), arithmetic mean, standard deviation (SD), median and range (minimum and maximum).

Categorical variables will be summarised by using frequency distributions and percentages.

The number of Adverse Events and the number and the percentage of patients experiencing those events, will be summarised by treatment group. Differences between groups will be evaluated using Chi-square test or Fisher's exact test. Subgroup analysis of differences between groups of AEs will be performed separately for patients who had an adverse event while on the 10mg dose (AE started from Visit 2 and Visit 3), 20 mg dose (AE started from Visit 3 and Visit 4) and 30 mg dose (AE started from Visit 4 and Visit 6). Subjects with adverse events who deviated from the protocol dosage will be highlighted in the footnotes.

Shift tables will be used to describe the evaluation of clinical significance for laboratory values, 12-Lead ECG and physical examination.

For all analyses, hypothesis testing will be carried out at the alpha = 0.05 level (two-sided) when comparing treatments. P-values will be rounded to three decimal places. Statistical significance will be declared if the rounded p-value will be less than or equal to 0.05.

Efficacy

For the PP efficacy analysis of incontinence episodes, only valid efficacy endpoints at Visit 6 will be used. For the ITT efficacy analysis of incontinence episodes, valid and imputed endpoints at Visit 6 will be used. The imputation method is described in section 6.1. No LOCF from baseline will be used for any efficacy analysis.

Descriptive statistics will be provided for all variables in the summary tables by treatment group according to the type of variable summarised.

Quantitative variables will be summarised by using n (number of subjects per group), arithmetic mean, standard deviation (SD), median and range (minimum and maximum).

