6.4 Patient Disposition

Disposition of patients will be presented by treatment group and overall for all patients.

The number of patients included in each of the randomised, safety, ITT, and PP populations will be summarised for each treatment group and overall.

Randomised patients who discontinued from the study prematurely will also be presented with a breakdown of the reasons for discontinuation by treatment group and overall for the randomised population.

Major and minor protocol violations will be presented in the listings only.

The number of patients who need a dose reduction will be presented with means of descriptive statistics. Frequencies and percentages will be used to describe the number of subjects who took a given amount of study drug (10/20/30 mg) at each visit.

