6.9.1 Sensitivity Efficacy Analyses

For the Efficacy Analyses relating to the number of incontinence episodes, a sensitivity analysis without imputation will be performed.

The sensitivity analyses will be performed on the ITT only, since the imputation method is not used in the PP population.

As with the Efficacy Analysis, baseline for all sensitivity endpoints will be defined as the last week of the Screening Placebo Run-In Period. The final measurement (endpoint) will be defined as Week 8 (Visit 6).

A second set of sensitivity analysis compares the placebo group with the patients in the litoxetine arm at 30 mg who did not have a dose reduction.

A third set of tables will analyse the absolute change of the number of incontinence episodes in a week and the percentage change in the number of incontinence episodes/24 hours.

1. Percentage change from end of the Screening Placebo Run-In Period to Week 8 (Visit 6) in the number of incontinence episodes in a week (without imputation)

This sensitivity analysis will use an ANCOVA model. It will follow the efficacy analysis described in section 6.9 point 1.

The imputation method will not be applied.

2. Change from end of the Screening Placebo Run-In Period to Week 8 (Visit 6) in the number of incontinence episodes/24 hours (daily average) (without imputation)

The change in the total number of incontinence episodes in a week will be analysed with an ANCOVA model. It will follow the efficacy analysis described in section 6.9 point 2.

The imputation method will not be applied.

3. Percentage change from end of the Screening Placebo Run-In Period to Week 8 (Visit 6) in the number of incontinence episodes in a week for patients without a dose reduction

The percentage change in the total number of incontinence episodes in a week will be analysed with an ANCOVA model. It will follow the efficacy analysis described in section 6.9 point 1. In the litoxetine group, only patients who did not have a dose reduction will be considered. Therefore, subjects who are dispensed the 30 mg dose at visit 5 will be considered in the litoxetine group.

4. Change from end of the Screening Placebo Run-In Period to Week 8 (Visit 6) in the number of incontinence episodes/24 hours (daily average) for patients without a dose reduction

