The change in the total number of incontinence episodes/24 hours will be analysed with an ANCOVA model. It will follow the efficacy analysis described in section 6.9 point 2. In the litoxetine group, only patients who did not have a dose reduction will be considered. Therefore, subjects who took the 30 mg dose at visit 6 will be considered in the litoxetine group.

5. Percentage change from end of the Screening Placebo Run-In Period to Week 8 (Visit 6) in the number of incontinence episodes/24 hours (daily average)

This exploratory analysis will use an ANCOVA model. It will follow the efficacy analysis described in section 6.9 point 1.

The number of incontinence episodes/24 hours (daily average) will be used as endpoint.

6. Change from end of the Screening Placebo Run-In Period to Week 8 (Visit 6) in the number of incontinence episodes in a week

The change in incontinence episodes in a week will be analysed with an ANCOVA model. It will follow the efficacy analysis described in section 6.9 point 2.

The total number of incontinence episodes in a week will be used as endpoint.

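### SAP 6.9.1 points 3 and 4 apply one no-dose-reduction criterion by two different visit rules, and the Visit 5 dispensing that point 3 uses is blank in both schedule tables

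*Protocol*

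**What the plan says.** **Analysis rule.** SAP 5.4.1 and the introduction to SAP 6.9.1 describe one comparison: placebo against litoxetine subjects at 30 mg with no dose reduction. Point 3 (percentage change) and point 4 (absolute change) each repeat that restriction, then say how to apply it. In point 3, "subjects who are dispensed the 30 mg dose at visit 5 will be considered in the litoxetine group". In point 4, "subjects who took the 30 mg dose at visit 6 will be considered in the litoxetine group".

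**Population.** SAP 6.9.1 adds: "The sensitivity analyses will be performed on the ITT only, since the imputation method is not used in the PP population". SAP 6.3 says: "For the ITT efficacy analysis of incontinence episodes, valid and imputed endpoints at Visit 6 will be used". Imputation is switched off by name only in points 1 and 2.

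**Visit 5 drug handling.** Protocol section 7.1.5 (Day 35) lists "Collect unused study drug and perform drug accountability" and "Dispense study drug". In Appendix 2 the row "Dispensing/collection of trial drug" is marked at Visits 1, 2, 3, 4, 6 and 7 and is empty at Visit 5. SAP Figure 1 has the same pattern. The only footnote on that row concerns the taper supply at Visit 6. SAP 6.4 also plans to tabulate "the number of subjects who took a given amount of study drug (10/20/30 mg) at each visit".

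**The concern.** The two points carry the same label and are meant to differ only in endpoint. If they select subjects differently, a difference between their results could come from who is in the litoxetine group and not from percentage versus absolute change. Point 3 can also admit the very subjects it is meant to leave out, because its test is made early in the 30 mg period.

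The blank cell matters because point 3 is built on a Visit 5 dispensing record. Section 7.1.5 lists the procedures but sends the site to the schedule for their timing, and the schedule has nothing in that cell. A site working from the table could make no Visit 5 record. Its subjects would then fail the point 3 rule even if they stayed on 30 mg throughout.

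**Working it through.** **1. Is the blank real?** The drug row has eight cells (Visits 1 to 5, telephone contact, Visits 6 and 7), and only Visit 5 and the telephone contact are empty. The vital-signs, ECG and adverse-event rows keep their Visit 5 marks, and the protocol and SAP tables agree. It is not a shifted column.

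**2. How much of the 30 mg period does the point 3 rule see?** Inputs from Appendix 2: 30 mg starts at Visit 4 (Day 28); Visit 5 is Day 35; Visit 6 is Day 70.
- Planned time at 30 mg: 70 − 28 = 42 days.
- Seen by Visit 5: 35 − 28 = 7 days.
- After Visit 5: 70 − 35 = 35 days; 35/42 = 83%.
- With the ±2-day window of section 7.1, the unseen stretch is 68 − 37 = 31 to 72 − 33 = 39 days.

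Protocol section 3.1 allows reduction from 30 to 20 mg BID for intolerance and sets no latest day for it.

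**3. Who is selected under each clause?** All are litoxetine subjects who started 30 mg at Visit 4.

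| Course | No reduction? | Point 3 clause | Point 4 clause |
|---|---|---|---|
| 30 mg to Visit 6, dispensed at Visit 5 | yes | in | in |
| Reduced by Day 35 and kept at 20 mg | no | out | out |
| Reduced between Day 35 and Day 70 | no | **in** | out |
| Withdrew between Visits 4 and 5 on 30 mg, early termination visit recorded | yes | out | in |
| Withdrew after Visit 5 on 30 mg, early termination visit recorded | yes | in | in |
| Withdrew after Visit 5 on 30 mg, no such record | yes | in | out |
| 30 mg to Visit 6, site made no Visit 5 dispensing record | yes | **out** | in |

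Withdrawn subjects count because these are ITT analyses with imputed Visit 6 values.

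**4. How many subjects?** The documents give no reduction rate and no timing of reductions or withdrawals. The litoxetine arm is about 78 × 2/3 = 52. As a what-if only, if 0%, 5%, 10% or 20% of the arm were reduced after Visit 5, the count is 0, 2.6, 5.2 or 10.4. For withdrawals after Visit 5 the lower limit is also zero, since a subject with 30 mg recorded at an early termination Visit 6 is classified alike by both clauses.

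**5. Reach.** The differing clauses affect points 3 and 4, two of the six listed analyses. The missing mark bears on point 3 and on the Visit 5 part of the dose table in SAP 6.4.

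**The case against.** The best reply is that the SAP has one criterion, not two. Both points first restrict the litoxetine arm to subjects without a reduction. Applied strictly, that sentence removes anyone reduced after Visit 5 from both analyses, and the third row of the table disappears. This is right about intent. It does not settle execution: the clause that follows is presented as the consequence of the criterion and is the one a programmer can code. In point 3 it admits a subject whom the sentence before it excludes.

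A second reply is that no dispensing is scheduled between Visits 5 and 6, and that Visit 6 issues only the half-dose taper. Dose taken at Visit 6 may then simply mean the supply issued at Visit 5, and the clauses agree unless the dose changes between visits. That is a fair reading, and it is one reason the affected number may be zero. But nothing confines reductions to scheduled visits.

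A third reply is that the blank cell is clerical, because section 7.1.5 is explicit. That largely stands. Section 5.5 requires every dispensing to be documented, and adverse-event records capture dose reduction as an action taken.

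A reader might infer more than this. One could conclude that the point 3 group would be empty, or that subjects would run out of drug: at four capsules a day (SAP 5.2), the interval from Visit 4 to Visit 6 needs 42 × 4 = 168 capsules. The documents do not support either. The rest of the text points to dispensing at Visit 5, and the quantity issued per visit is not stated.

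**Conclusion.** The inconsistency holds and is minor. One criterion is put into practice by two rules. The point 3 rule is blind to about 83% of the planned 30 mg period and rests on a dispensing that both schedule tables omit. The two analyses can therefore use different litoxetine subjects under the same description.

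The size in subjects is not known. The what-if counts rest on assumed rates, and a reader should not take them as an estimate that a material share of the arm would be misclassified; none may be. Nor do the documents support a wider effect. These are sensitivity analyses of secondary endpoints, compliance is computed over Visits 2 to 6 as a whole, and the primary safety analysis, the sample size and the main efficacy analyses do not use either rule.

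**What to change.** 1. Replace the applying clause in SAP 6.9.1 points 3 and 4 with one rule: litoxetine subjects who started 30 mg BID at Visit 4 and have no reduction below 30 mg BID recorded in the eCRF dosing or dispensing data, or as an adverse-event action taken, up to Visit 6 or the last treatment-period visit. Starting from Visit 4 avoids making the doubtful Visit 5 record a condition of entry. If subjects who withdrew before a given visit are to be left out, say so and apply the same exclusion to placebo, so that early dropouts are not removed from one arm only.
2. Add a mark at Visit 5 in the trial-drug row of Appendix 2 and SAP Figure 1, to match section 7.1.5. The pregnancy-test and concomitant-medication cells are also blank there; these are clerical corrections only, since Appendix 2 footnote 6 and section 5.6 already require both.

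The cost is one shared definition, up to three cells in each of two tables, and a note to sites. No visit, procedure or data item is added.

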Appendix 3: New York Heart Association Heart Failure Classification

Class	Patient Symptoms
I	No limitation of physical activity. Ordinary physical activity does not cause undue fatigue, palpitation, dyspnoea (shortness of breath).
II	Slight limitation of physical activity. Comfortable at rest. Ordinary physical activity results in fatigue, palpitation, dyspnoea (shortness of breath).
III	Marked limitation of physical activity. Comfortable at rest. Less than ordinary activity causes fatigue, palpitation, or dyspnoea.
IV	Unable to carry on any physical activity without discomfort. Symptoms of heart failure at rest. If any physical activity is undertaken, discomfort increases.

Appendix 4: Psychiatric monitoring: Columbia-Suicide Severity Rating Scale (C-SSRS), Beck Depression Inventory-II (BDI-II), Beck Anxiety Inventory (BAI), Pittsburgh Sleep Quality Index (PSQI)

12.	Appendix 3	39
13.	Appendix 4	39
14.	Appendix 5	39

List of abbreviations and definitions of terms

Abbreviation	Definition
AE	Adverse event
AESI	Adverse event of special interest
BID	Twice daily
CYP	Cytochrome P450
DA	Dopamine
EC	Ethics Committee
ECG	Electrocardiogram
eCRF	Electronic case report form
EDC	Electronic data capture
ICS	International Continence Society
IRAE	Immediately reportable adverse event
ITT	Intent-to-treat (population)
MACR	Missing completely at random
MMRM	Mixed-Effect Model for Repeated Measure
MedDRA	Medical Dictionary for Regulatory Activities
MUI	Mixed urinary incontinence
NE	Norepinephrine
NHS	National Health Service
PP	Per Protocol (population)
PVR	Postvoid residual volume
SAE	Serious adverse event
SAP	Statistical Analysis Plan
SNRI	Serotonin and norepinephrine reuptake inhibitor
SSRI	Selective serotonin reuptake inhibitor
SUI	Stress urinary incontinence
TEAE	Treatment-emergent adverse event
UI	Urinary incontinence
UK	United Kingdom

Abbreviation	Definition
US	United States
UUI	Urge urinary incontinence
WBC	White blood cell (count)
WHO	World Health Organisation

1. Introduction

This Statistical Analysis Plan (SAP) describes the statistical analysis for IXA-CSP-002 study based on study protocol IXA-CSP-002-protocol amendment 2 issued Oct 10, 2018.

1.1 Background

Urinary incontinence (UI) is a common and chronic condition affecting both males and females, although it is more commonly seen in women. For both genders, prevalence increases with age, occurring frequently in the geriatric population (65 years and older) (Adams P, 2010). Urinary incontinence, which is defined by the International Continence Society (ICS) as involuntary loss of urine", is estimated to affect 400 million people worldwide (Fultz NH, 2003; Global Forum on Incontinence). Prevalence varies greatly with age and the definition used, and has been reported to be as high as 55%. Not all affected need medical treatment.

This condition is often underreported since many people avoid discussing the problem with their doctor due to embarrassment, lack of knowledge about treatment options, or a belief that urinary incontinence is an inevitable part of ageing.

While not life-threatening, urinary incontinence can have a significant negative impact on the psychological well-being, social functioning and overall quality of life of those affected, resulting in social reclusion and also an economic burden.

The burden of urinary incontinence is high in financial terms, with the total annual cost of urinary incontinence in the United States (US) estimated to be as high as \$32 billion (Wood LN, 2014). Total cost of managing urinary incontinence in women over the age of 40 years in the United Kingdom (UK) in 2004 was £301 million, 0.3% of the total National Health Service (NHS) budget (Turner DA, 2004). Costs borne by women in out-of-pocket expenses was £230 million (Fultz NH, 2003) or £290 per woman per year (Papanicolaou S, 2005).

Women suffer most commonly from stress urinary incontinence (SUI) or a combination of SUI and urge urinary incontinence (UUI) i.e. Mixed Urinary Incontinence (MUI). Men suffer primarily from urgency, due to obstruction from prostate hypertrophy, and have a higher incidence of 'dry' symptoms (urgency, frequency without urinary incontinence). Stress incontinence in men accounts for less than 10%, mainly occurring post prostate surgery (Adams P, 2010).

Urinary incontinence can be managed initially by lifestyle modifications, with reduction of excessive fluid intake, timed voiding, weight loss if required, and bladder and pelvic floor muscle training. Drug treatments are available for over-active bladder, with anticholinergic drugs the mainstay of treatment for cases that do not respond to lifestyle modification. Several agents are currently available including oxybutynin, tolterodine, fesoterodine, trospium, solifenacin, and darifenacin.

Many women are unable to tolerate anticholinergic drugs and 30-91% discontinue them after 1 year. If patients do not respond to a treatment attempt of anticholinergic drugs, minimally invasive treatment options are available, with intravesical injection of onabotulinum toxin A, sacral neuromodulation, and posterior tibial nerve stimulation available as potential options.

Serotonin plays an important role in centrally modulating the reflexes of continence/micturition; 5-HT potentiates the guarding reflex which allows continence by increasing urethral pressure and inhibits the micturition reflex responsible for voiding. Animal studies have shown that increased levels of 5-HT and norepinephrine (NE), in the sacral spinal cord, lead to increased urethral tone via enhanced pudendal nerve stimulation to the urethral striated sphincter muscle during the storage phase of the micturition cycle. Studies with duloxetine support a similar mechanism in women, believed to result in stronger urethral closure during urine storage with physical stress.

Animal studies have confirmed that litoxetine increases the urethral sphincter pressure, and also demonstrated that litoxetine improves bladder capacity through a relaxation effect of the detrusor. Taken together these effects suggest that litoxetine could have therapeutic benefit in Urinary Incontinence, a condition for which there is a high unmet medical need.

The 5-HT selectivity of litoxetine, and the weaker affinity for NE and epinephrine (E) as well as for dopamine (DA) transporters has the potential to provide a good cardiovascular safety profile, and reduce the risk of nausea which is the most frequent side effect following treatment with 5-HT reuptake inhibitors.

Further details can be found in the Investigator's Brochure (Edition 3, Feb 2018), which contains comprehensive information on the investigational product.

